9.2.8 Patient 's dose change/ dose interruption

The recommendations in the product information for ropeginterferon alfa-2b dosing (including dose changes or temporarily treatment interruption) should be followed (Annex 1). Any ropeginterferon alfa-2b dose change/interruption has to be documented including the reason for

dose change/interruption. A temporary ropeginterferon alfa-2b treatment interruption is no reason for study discontinuation.

9.2.9 Patient completion

A patient is considered to have completed the study when he/she ceases active participation in the study because the patient has, or is presumed to have, completed all study procedures according to the protocol (see Figure 1).

Completion will be documented on the respective eCRF page, including the reason for completion (e.g. study completed, screening failure, adverse event occurrence [e.g. death], study discontinuation (section 9.2.7)). Regardless of the reason, all data available for the patient up to the time of completion should be recorded on the appropriate eCRF pages.

9.3. Variables

9.3.1 Safety Variables

9.3.1.1 Adverse events of special interest

• Hepatotoxicity³ during study participation:

- Clinically significant elevations of ALT, AST, GGT (≥3 times ULN) and/or bilirubin (> 2 times ULN)
- Treatment-emergent hepatobiliary adverse drug reactions

• Cardiovascular adverse events:

- Thromboembolic adverse events
- MACE [i.e. nonfatal stroke, nonfatal myocardial infarction and cardiovascular death]

Diagnostic procedures will be conducted according to the needs of the patients, and parameters of standard assessments will be monitored in this study and entered in the eCRF as available (Table 1). Definition of treatment-emergent adverse events and treatment-emergent adverse drug reactions is included in Section 11.1.1.

9.3.1.2 Other safety variables

- All treatment-emergent adverse events

9.3.2 Evaluation of risk minimization measures

- Frequency of evaluation of hepatic enzymes (AST, ALT, GGT) and bilirubin in clinical routine
- Hepatobiliary adverse events after dose reduction or treatment discontinuation due to significant elevations of liver enzymes ALT, and/or AST, and/or GGT (≥3 times ULN) and/or bilirubin (>2 times ULN)
- Dose adjustments or treatment discontinuations due to hepatotoxicity
- Hepatic enzymes (AST, ALT, GGT) and bilirubin after dose reduction or treatment discontinuation due to significant elevations of ALT, AST, GGT (≥3 times ULN) and/or bilirubin (> 2 times ULN)
- Follow-up of hepatobiliary AEs after dose reduction or treatment discontinuation due to Treatment-emergent hepatobiliary adverse drug reactions

Important identified risk in the ropeginterferon alfa-2b Risk Management Plan.

 Number of patients with hepatobiliary adverse events after significant elevations of liver enzymes ALT, and/or AST, and/or GGT (≥3 times ULN) and/or bilirubin (>2 times ULN)

9.3.3 Demographics

At baseline, the patient's demographics will be collected for the following according to routine clinical practice:

- Age
- Gender
- Weight [kg]
- Height [cm]
- Body mass index [kg/m²], calculated
- Blood pressure
- Heart rate

9.3.4 Medical History

At baseline, the patient's clinically relevant medical history will be collected for the following:

- PV disease history (date of diagnosis, criteria of diagnosis)
- Assessment of cardiovascular risk-factors⁴
- Assessment of pre-existing liver disease (yes/no, details)
- Assessment of pre-existing cardiac disease (yes/no, details)
- · Assessment of previous thromboembolic events (yes/no, details)
- Assessment of alcohol intake (yes/no, details)

During study participation, the following information on medical history will be collected:

 Any medical history relevant for the characterization of treatment emergent adverse events

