2. Secondary objectives

- To describe the baseline characteristics of PV patients newly treated with ropeginterferon alfa-2b in routine post-authorization use.
- To evaluate the effectiveness of the risk minimization measures for the important, identified risk "hepatotoxicity".

- To further characterize the important, identified risk "hepatotoxicity" in subgroups of the patient population (i.e. with/without co-medication with nonsteroidal anti-inflammatory drugs, with/without pre-existing liver disease or baseline liver parameter elevation).
- To assess the incidence rate of thromboembolic adverse events and major adverse cardiac events (MACE) in PV patients newly treated with ropeginterferon alfa-2b in routine post-authorization use.
- To further evaluate cardiovascular safety in subgroups of the patient population (i.e. with/without cardiovascular risk factors, with/without pre-existing cardiovascular disease).

9. Research methods

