9.2.3.1 Inclusion and exclusion criteria

The study will include approximately 228 adult PV patients. The inclusion and exclusion criteria are listed below.

• Inclusion criteria:

- 1. Patients who receive ropeginterferon alfa-2b in the frame of clinical routine and according to its approved labelling: monotherapy in adults (≥ 18 years old) for the treatment of PV without symptomatic splenomegaly and according to the recommendations in the product information for ropeginterferon alfa-2b (Annex 1)
- 2. Patient's medical history is available
- 3. Patient provides written informed consent prior to study entry

• Exclusion criteria:

- 1. Patients with any contraindication to ropeginterferon alfa-2b treatment according to the product information for ropeginterferon alfa-2b (Annex 1)
- 2. Patients involved in any study with another investigational product or therapy (in the prior 30 days)
- 3. Previous ropeginterferon alfa-2b treatment
- 4. Patient is a family member or employee of the Investigator

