9.2.4 Informed consent and enrolment

Any volunteer who provides informed consent (i.e. signs and dates the informed consent form) is considered enrolled in the study (Section 10.5).

² PV disease history, cardiovascular risk-factors, pre-existing liver disease, pre-existing cardiac disease.

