9.3.5 Concomitant Medication

At baseline, the following information will be collected:

Previous treatment for PV

During study participation, the following information on concomitant medication will be collected:

- Non-steroidal anti-inflammatory drugs
- Medication assessed by the investigator to impact hepatic parameters
- Cardio-vascular medication

⁴ Unhealthy lifestyle (cigarette smoking, physical inactivity, diet high in fat); high risk diseases (hypertension, obesity, dyslipidaemia, diabetes)

• Any medication relevant for the characterization of treatment emergent adverse events

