9.7.2.5 Additional subgroup analyses

- Subgroup analysis of incidence of significant elevations of liver enzymes and bilirubin for patients with and without co-medication with nonsteroidal anti-inflammatory drugs
- Subgroup analysis of incidence of significant elevations of liver enzymes and bilirubin for patients with and without pre-existing liver disease/or patients with baseline liver parameter elevation
- Subgroup analysis of incidence of treatment-emergent hepatobiliary adverse drug reactions for patients with and without co-medication with nonsteroidal anti-

inflammatory drugs

- Subgroup analysis of incidence of treatment-emergent hepatobiliary adverse drug reactions for patients with and without pre-existing liver disease/or patients with baseline liver parameter elevation
- Subgroup analysis of incidence of cardiovascular events (i.e. thrombo-embolic adverse events and MACE) for patients with and without cardiovascular risk factors
- Subgroup analysis of incidence of cardiovascular events (i.e. thrombo-embolic adverse events and MACE) for patients with and without pre-existing cardiovascular disease

Absolute and relative frequencies of patients with treatment emergent adverse events, count and incidence rate (including two-sided 95% CIs) of events overall and by MedDRA primary System Organ Class and Preferred Term will be calculated.

In addition, tables will be prepared to list each serious and non-serious adverse event, the number of patients who experience an event at least once, and the proportion of patients with adverse events/serious adverse events/adverse events of special interest.

Adverse events will be grouped by system organ class (SOC). Each event will be then divided into defined intensity grades (mild, moderate, and severe) by the Investigator. The tables will also divide the adverse events into those considered related to treatment (ropeginterferon alfa-2b) and those not related, as well as adverse events considered related to underlying disease PV.

The statistical analysis will be done in agreement with the ICH Topic E9, Statistical Principles for Clinical Trials and Statistical Analysis Plan (SAP) finalized and approved by the Sponsor and the study statistician before database lock. Analyses will be conducted using Statistical Analysis System (STATA®) software,

by using the last version of the dictionaries available at that timepoint.

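### The subgroup split by pre-existing cardiovascular disease has no matching baseline item: non-cardiac vascular disease without a prior event is not asked for, so such patients can be counted as without disease

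*Protocol*

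**What the plan says.** The last secondary objective in Protocol Section 8 is to evaluate cardiovascular safety in subgroups "with/without cardiovascular risk factors, with/without pre-existing cardiovascular disease". Section 9.7.2.5 carries this into two analyses of thromboembolic events and MACE, one "for patients with and without cardiovascular risk factors" and one "for patients with and without pre-existing cardiovascular disease".

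The baseline history in Section 9.3.4 contains three items that bear on this:

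- cardiovascular risk factors, which footnote 4 defines as lifestyle factors plus "high risk diseases (hypertension, obesity, dyslipidaemia, diabetes";
- "Assessment of pre-existing cardiac disease (yes/no, details";
- "Assessment of previous thromboembolic events (yes/no, details".

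Footnote 2, printed under Section 9.2.4, summarises the history as "PV disease history, cardiovascular risk-factors, pre-existing liver disease, pre-existing cardiac disease". It also says cardiac, and it does not mention thromboembolic history.

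Section 9.7.2.5 does not say which baseline items place a patient in the group with pre-existing cardiovascular disease.

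**The concern.** The subgroup variable is wider than the baseline item that most resembles it. Cardiac disease is one part of cardiovascular disease; cerebrovascular and peripheral vascular disease are others. The hepatic side of the same protocol shows no such gap: the objective, the baseline item and the subgroup analysis all refer to pre-existing liver disease.

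The outcome in this subgroup is thromboembolic events and MACE, so patients with vascular disease are plausibly among those at highest risk. Counting some of them as without disease raises the event rate in that group and pulls the comparison towards no difference. Cardiovascular safety is one of the two stated purposes of the study, and Section 7 calls thromboembolic events a major risk of the disease. A variable that was not collected for everyone at baseline cannot be reliably rebuilt at the analysis stage.

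**Working it through.** No figure in the protocol depends on this point, so there is nothing to reproduce. The first step compares the text; the second illustrates the size on assumed inputs.

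**Step 1: where each type of patient is recorded.**

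| Patient | Cardiac item | Thromboembolic item | Risk-factor item (footnote 4) |
|---|---|---|---|
| Cardiac disease | yes | only if prior event | not covered |
| Prior stroke, deep vein thrombosis or pulmonary embolism, no cardiac disease | not on a plain reading | yes | not covered |
| Peripheral arterial or carotid disease, no prior event | not on a plain reading | no | not covered |

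The second row is recorded and can be recovered by combining two items. The third row has no item.

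**Step 2: dilution, as an illustration.** Let *p* be the share of patients with cardiovascular disease, *m* the share who have it but are counted as without, and *r1* and *r0* the event risks with and without it. Missed patients are assumed to have the same risk *r1* as those correctly counted. Then:

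risk in the recorded group without disease = [*m* × *r1* + (1 − *p*) × *r0*] / (*m* + 1 − *p*)

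Assumed, because the documents give none of these: *p* = 30%, *r1* = 8%, *r0* = 2% over 18 months. True ratio 8/2 = 4.0.

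- *Only event-free vascular disease missed (assume m = 3 points, about 7 of 228 patients):* (0.03 × 8% + 0.70 × 2%) / 0.73 = 2.25%. Ratio 8/2.25 = 3.6.
- *Thromboembolic history also ignored and half missed (assume m = 15 points, about 34 of 228):* (0.15 × 8% + 0.70 × 2%) / 0.85 = 3.1%. Ratio 8/3.06 = 2.6.

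**Range on other assumptions, if the cardiac item alone defined the subgroup.** Take cardiac disease in 10 to 20% of patients, vascular disease only in 5 to 20%, and *r0* = 3%:

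| True risks | True ratio | Ratio observed |
|---|---|---|
| 10% against 3% | 3.33 | 2.11 to 2.95 |
| 6% against 3% | 2.0 | 1.60 to 1.89 |

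Between 228 × 0.05 = 11 and 228 × 0.20 = 46 patients would be misplaced, making up 6% to 25% of the recorded group without disease. The direction is always towards no difference.

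**Precision.** On the first set of assumptions, with no dropout and perfect classification, 228 patients give 228 × 0.30 × 8% = 5.5 events with disease and 228 × 0.70 × 2% = 3.2 without, about 9 in all. The standard error of the log ratio is √(1/5.47 − 1/68.4 + 1/3.19 − 1/159.6) = 0.69, so an approximate 95% interval around 4.0 runs from 1.0 to 15.

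**The case against.** A reader might infer that every patient with a prior stroke, deep vein thrombosis or pulmonary embolism will be counted as without disease. The documents do not support that. Nothing says that the cardiac item alone defines the subgroup. Section 9.3.1.1 builds cardiovascular adverse events from thromboembolic events and MACE, and Section 9.3.4 collects a similar pair at baseline, so combining the two items is a natural reading. A statistical analysis plan could say so, and mapping recorded items to a subgroup is ordinary content for one. This part of the objection stands: for these patients the protocol is silent, not wrong.

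It does not reach patients with event-free peripheral arterial or carotid disease, because an analysis plan cannot supply data that no baseline item requests. Some partial safeguards exist: available medical history is an entry criterion, the items have room for details, and cardiovascular medication is recorded. But medication is not a diagnosis, and the protocol does not tie any of these to the subgroup. Further history during the study is collected only where it is relevant to characterising an adverse event, so it would reveal vascular disease selectively in patients who had one. Reclassifying on that basis would make the subgroup depend on the outcome.

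It can also be said that cardiac is meant broadly, since the MACE definition includes stroke. That is possible, but thromboembolic history is a separate entry in the same list, which invites a narrow reading. At best, sites may answer differently. Footnote 2 is weak evidence either way: it looks like shorthand for the entry criterion on available history and also leaves out alcohol intake, which Section 9.3.4 collects.

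A second tempting inference is that the study would wrongly conclude that events are equally common in both groups. The illustration does not show this: even its worse case leaves a ratio of 2.6. With about 9 events, the study could not tell 2.6 from 4.0.

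**Conclusion.** The mismatch is real and on the face of the protocol, but narrow. Event-free non-cardiac vascular disease has no baseline item, so these patients can be counted as without pre-existing disease. Patients with a prior thromboembolic event are recorded, and their placement depends on a rule that the protocol does not state.

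The effect, if misplaced patients do have higher risk, is dilution of the subgroup contrast. Its size is unknown. A fall from 4.0 to about 3.6 illustrates the part that later analysis cannot reliably repair; about 2.6 applies only if the recorded thromboembolic history is also ignored and half of the affected patients are missed. Every prevalence and risk behind these figures is an assumption.

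One descriptive secondary subgroup is affected. The primary hepatotoxicity endpoint, the sample size and the overall cardiovascular incidence are not. The point is worth making because correction is cheap and concerns what is collected for a stated objective.

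**What to change.** 1. In Section 9.3.4, replace the cardiac item with: pre-existing cardiovascular disease (cardiac, cerebrovascular, peripheral vascular; yes/no, details). Align footnote 2 with it.
2. In Section 9.7.2.5, state that a patient belongs to the group with pre-existing cardiovascular disease if the answer is yes to this item or to previous thromboembolic events.

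The cost is one eCRF label with its categories, one footnote and one sentence. The information comes from the medical record and needs no procedure, so the only downside is slightly more baseline data entry. A separate split by previous thromboembolic event is possible because the item is already collected, but the objectives do not ask for it and it is optional.

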9.3.5 Concomitant Medication

At baseline, the following information will be collected:

Previous treatment for PV

During study participation, the following information on concomitant medication will be collected:

- Non-steroidal anti-inflammatory drugs
- Medication assessed by the investigator to impact hepatic parameters
- Cardio-vascular medication

⁴ Unhealthy lifestyle (cigarette smoking, physical inactivity, diet high in fat); high risk diseases (hypertension, obesity, dyslipidaemia, diabetes)

• Any medication relevant for the characterization of treatment emergent adverse events

9.3.6 Other PV-related treatments and procedures

- Dosing ropeginterferon alfa-2b
- Concomitant PV-treatment (other than ropeginterferon alfa-2b)
- Phlebotomy

Table 1. Parameter assessment during ropeginterferon alfa-2b PASS Part A and Part B.

Activity/ Assessment	Eligibility#	Baseline*,#	Part A#	Part B#
Inclusion/Exclusion criteria	Х			
Medical history		Х		
Demographics		Х		
Ropeginterferon alfa-2b administration		Х	Х	Х
Clinical laboratory: Hematology ¹ Chemistry ²		X	X X**	X X**
Concomitant medication Phlebotomy performed		X	X	X
Adverse events of special interest: - Treatment-emergent hepatobiliary adverse drug reactions - Thromboembolic adverse events - Major adverse cardiac events (MACE)			X X X	x x x
All treatment-emergent adverse events			Х	Х

^{*}defined as 1st ropeginterferon alfa-2b administration within study.

9.4. Data sources

Source data are defined as all the information related to clinical findings, observations, or other activities in the study, written down in original records or certified copies of original records allowing reconstruction and evaluation of the study. Source data are contained in source documents (original records or certified copies), which may be in paper and/or electronic format, can comprise the following (but not limited): hospital records, medical records, clinical and office charts, laboratory notes, and memoranda.

The Investigator will ensure that the eCRF is correctly completed. The eCRF will be

^{**} for hepatotoxicity assessment in Part A and Part B; see Section 9.2.6.

[#]assessed during routine clinical practice.

¹ Laboratory parameters: Haemoglobin (Hb), haematocrit, platelets, red blood cells, white blood cells.

² Laboratory parameters: Hepatic parameters (alanine aminotransferase [ALT], aspartate aminotransferase [AST], gamma-glutamyl transferase [GGT], total bilirubin).

electronically signed by the Investigator signifying agreement with and responsibility for the recorded data.

9.5. Study size

The primary endpoint of the Besremi-PASS study is the incidence of clinically significant increases of liver enzymes or bilirubin during part A of the study, i.e., within 6 months. Results of the PROUD-PV study suggest an incidence of 23.6% for clinically significant increases of liver enzymes or bilirubin within one year. Thus, an incidence of 12.6% for clinically significant increases of liver enzymes or bilirubin can be expected during Part A. Therefore, in a sample of 169 patients, an observed incidence rate of 7.5 - 17.4% can be expected with a probability of 95%, resulting in 95% confidence interval $\leq 10\%$, if the confidence intervals are estimated according to Wald. If the more conservative exact estimation is used, a sample of 186 patients is expected to result in an incidence rate of 8.0 - 18.0% (95% confidence interval $\leq 10\%$). Thus, the inclusion of 178 evaluable patients, i.e., the median of 169 and 186, is envisaged.

In the Besremi-PASS study patients shall be observed for 18 months. During the Proud-PV study a drop-out rate of 20% was observed over one year. Thus, a dropout rate of 28.5% is assumed for 18 months. Therefore, a total of 228 patients is required in order to observe 178 evaluable patients for the entire study period of 18 months.

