9.9. Limitations of the research methods

Data are captured in real-world setting. Patients may be exposed to a multitude of other medical procedures, are aware of their treatment and are not compared to a control group. Due the observational nature of the study, it should be taken into consideration that there might be incomplete datasets among the participating centres.

The Sponsor has selected approximately 10 Sites in Austria and 15 sites in Germany, covering a large proportion of the pool of suitable patients in both countries, to participate in this study. In the unlikely case of slow recruitment, the Sponsor will evaluate the inclusion of additional sites and assess the possibility of adding sites in additional countries, depending on the status of commercialization of Besremi.

The primary endpoint of the Besremi-PASS study is the incidence of significant elevations of liver enzymes ALT, and/or AST, and/or GGT (≥3 times ULN) and/or bilirubin (>2 times ULN), and (2) treatment-emergent hepatobiliary adverse drug reactions in the first 6 months of treatment. A dropout rate of 20% over one year was observed in the PROUD-PV study, from which a dropout rate of 10% can be assumed after 6 months of treatment. The extrapolated dropout rate of 28.5% over 18 months used for sample size calculations is therefore highly conservative and will allow for evaluation of the primary endpoint even if dropout rates over 6 months of treatment are higher than expected.

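### The evaluable target of 178 averages a Wald size and an exact size, so it answers neither calculation and slightly misses the 10-point width under the exact interval

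*Protocol*

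**What the plan says.** Section 9.5 starts from a one-year incidence ("Results of the PROUD-PV study suggest an incidence of 23.6"%) and converts it to six months: "an incidence of 12.6% for clinically significant increases of liver enzymes or bilirubin can be expected during Part A". It then sizes the study on the width of a two-sided 95% confidence interval, to be at most 10 percentage points.

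Two sizes are given for that one goal:

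- Wald: "in a sample of 169 patients, an observed incidence rate of 7.5 - 17.4% can be expected with a probability of 95"%.
- Exact, introduced with "If the more conservative exact estimation is used": "a sample of 186 patients is expected to result in an incidence rate of 8.0 - 18.0"%.

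The section then concludes that "the inclusion of 178 evaluable patients, i.e., the median of 169 and 186, is envisaged". It arrives at 228 enrolled patients by allowing for dropout over 18 months. Section 9.7.2.1 places the primary endpoint in Part A, the first 6 months. For that time point section 9.9 says that "a dropout rate of 10% can be assumed after 6 months of treatment".

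**The concern.** The sizes 169 and 186 answer the same question under two alternative interval methods. One primary incidence will be reported with one interval, so one of the two sizes applies and the other does not. Their midpoint corresponds to no method: it is more than Wald needs and less than the exact method needs. The protocol labels the exact method the more conservative one, computes 186 for it, and then fixes a target below 186 without giving a reason.

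Interval width is the only argument section 9.5 offers for the evaluable number. If the exact interval is later chosen, the stated number falls short of the stated goal. If Wald is chosen, the 186 plays no part and neither does the average built on it.

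**Working it through.** **Inputs (section 9.5 unless noted).** One-year incidence 23.6%; six-month incidence 12.6%; full 95% width at most 10 points; sizes 169, 186 and 178; enrolment 228; six-month dropout 10% (section 9.9); dropout of 20% over one year.

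**1. Six-month incidence.** 1 − (1 − 0.236)^0.5 = 0.1259, or 12.6%. This reproduces the protocol.

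**2. Wald size.** n = z²p(1 − p)/0.05² = 1.96² × 0.126 × 0.874/0.0025 = 169.2. With 21 events in 169 patients (12.43%) the interval is 7.45% to 17.40%, a width of 9.95 points. This reproduces 169 and 7.5 to 17.4%.

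**3. Exact size (Clopper-Pearson, from beta quantiles).** With 23 events in 186 patients (12.37%) the interval is 8.00% to 17.97%, a width of 9.97 points. Taking the whole number of events nearest to n × 0.126, 186 is the first n at which the width is 10 points or less. This reproduces 186 and 8.0 to 18.0%.

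**4. Midpoint.** (169 + 186)/2 = 177.5, rounded to 178.

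**5. Width at 178.** The expected count is 178 × 0.126 = 22.4, so 22 and 23 events are the relevant whole numbers.

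| Interval | 22 events | 23 events | Expected width at 12.6% |
|---|---|---|---|
| Exact | 7.91 to 18.11%: 10.20 points | 8.37 to 18.76%: 10.38 points | 10.22 points |
| Wald | 9.67 points | 9.86 points | 9.69 points |
| Wilson | 9.70 points | 9.88 points | 9.72 points |

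Only the exact interval misses, by 0.2 to 0.4 points. At n = 186 its expected width is 9.99 points. Wilson and mid-P reach 10 points at about 169 to 170 patients, so they do not lead to 178 either.

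**6. Precision when the primary endpoint is read.** At 10% dropout, 228 × 0.90 = 205.2 patients remain. Converting 20% per year to six months gives 1 − 0.8^0.5 = 10.6% dropout, and 228 × 0.8^0.5 = 203.9. With 204 to 205 patients the expected exact width at 12.6% is about 9.5 points, within the goal.

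**The case against.** The strongest reply is that nothing is lost in practice. The 178 is attached to the full 18 months, while the primary endpoint is read at 6 months, when about 204 to 205 patients should be available. At that number every interval considered here is narrower than 10 points. Section 9.9 makes the same argument in words. This stands, and it rules out the reading that the precision of the primary incidence will not be delivered. On the protocol's own dropout assumption it will be.

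It is also fair to say that 178 satisfies the goal under two standard methods. A reader might infer that 178 fits no interval at all. That is true only of how the number was derived, not of the widths obtained at 178.

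A reader might further infer that a Wald interval at 178 would not be a 95% interval, because its coverage at exactly 12.6% is 93.2%. That figure is one point on a sawtooth produced by the discreteness of the binomial. At the same incidence, Wald coverage is about 95% at n = 186 and at n = 204. Nothing here rests on it.

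Nor should 178 be judged by the probability that the realised width stays within 10 points. The protocol sizes on the width at the expected incidence and sets no such criterion.

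Finally, the choice of interval to report may be left to the statistical analysis plan. That is accepted. What remains is that the protocol computes a requirement under a named method and then states a number that does not meet it.

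**Conclusion.** The point holds as a correction to the stated number and its rationale. The protocol's component figures all reproduce; the fault lies in averaging them. At 178 the exact width is 10.2 to 10.4 points against a goal of 10, which is 8 patients short of the protocol's own exact size. Wald and Wilson meet the goal at about 9.7 points.

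The consequence is small. The study is descriptive, section 9.5 attaches no test or decision threshold to the width, and planned enrolment covers the six-month analysis. This rests on a six-month incidence of 12.6%, dropout by month 6 of 10 to 10.6%, and counting only patients who have not dropped out as evaluable.

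**What to change.** In section 9.5, delete the averaging and tie the evaluable number to one interval method. Either:

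- state 186 evaluable patients for the exact interval; or
- keep 178, name Wilson, and state the width of about 9.7 points.

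Then add the precision at the time of the primary endpoint: about 204 to 205 of 228 patients at month 6, with an expected exact width of about 9.5 points.

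The cost is a few reworded sentences in section 9.5, kept consistent with the interval named in the statistical analysis plan. Part A needs no extra patients under either option: 186 evaluable at month 6 requires 186/0.90 = 206.7, so 207 enrolled at 10% dropout, below the planned 228. The wording should say that the number refers to month 6. How many of the 228 remain at 18 months is a separate calculation that this change does not settle.

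### Protocol 9.5: with the stated 28.5% dropout, 228 enrolled patients leave about 163 at 18 months, not the stated 178

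*Protocol*

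**What the plan says.** Section 9.5 sizes the study for the precision of one proportion: the incidence of clinically significant liver enzyme or bilirubin increases "during part A of the study, i.e., within 6 months". From an expected incidence of 12.6% and an interval of at most 10 points it obtains 169 patients (Wald) or 186 (exact), and settles between them: "Thus, the inclusion of 178 evaluable patients, i.e., the median of 169 and 186, is envisaged".

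It then allows for dropout. The source is the earlier phase III trial: "During the Proud-PV study a drop-out rate of 20% was observed over one year". This is carried forward to the planned follow-up: "Thus, a dropout rate of 28.5% is assumed for 18 months". The conclusion is "Therefore, a total of 228 patients is required in order to observe 178 evaluable patients for the entire study period of 18 months". The Abstract and section 9.2.3.1 repeat the figure of approximately 228.

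Section 9.9 returns to the subject. For the 6-month endpoint it takes the one-year rate, "from which a dropout rate of 10% can be assumed after 6 months of treatment", and adds: "The extrapolated dropout rate of 28.5% over 18 months used for sample size calculations is therefore highly conservative".

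**The concern.** A cumulative loss of 28.5% of those enrolled leaves 71.5%. An enrolment figure meant to leave 178 patients should therefore be 178 divided by 0.715, which is well above 228. Either the enrolment is too small for the stated yield, or the stated yield is too large for the enrolment.

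The number who complete 18 months determines the size of FAS2 (section 9.7.1). The secondary safety endpoints also run over the whole study period (9.7.2.2), as does the evaluation of the risk minimisation measures (9.2.6). A regulator or sponsor planning on 178 patients with complete follow-up would be planning on a number that the protocol's own inputs do not deliver. Section 9.9 also describes the dropout allowance as larger than the one actually built into 228.

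**Working it through.** **Inputs, all from the protocol.** Target evaluable 178, the midpoint of 169 and 186 (177.5, rounded up). Dropout 20% over one year and 28.5% over 18 months (9.5). Dropout 10% at 6 months (9.9). Enrolment 228. Expected 6-month incidence 12.6%.

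**Step 1. The extrapolated rates reproduce.** Under a constant hazard, 18-month dropout is 1 − 0.8^1.5 = 28.45%, matching the stated 28.5%. The same model applied to the one-year incidence of 23.6% gives 1 − 0.764^0.5 = 12.6% at 6 months, also as stated. The 28.5% is therefore a cumulative fraction of those enrolled.

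**Step 2. Where 228 comes from.**
- n × (1 + d): 178 × 1.285 = 228.7, and from the unrounded midpoint 177.5 × 1.285 = 228.1.
- n / (1 − d): 178 / 0.715 = 248.95, so 249.

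Other inputs in the dividing form do not return 228 either:

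| Target | Dropout | Enrolment |
|---|---|---|
| 178 | 30% (linear to 18 months) | 255 |
| 178 | 20% | 223 |
| 178 | 10% | 198 |
| 169 | 28.5% | 237 |
| 186 | 28.5% | 261 |

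Of the variants tried, only the multiplying form gives 228. It does so exactly from 177.5; from 178 it needs rounding down. Since no formula is shown, this remains a likely explanation and not a documented one.

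**Step 3. What 228 delivers at 18 months.** 228 × 0.715 = 163.0. The shortfall is 178 − 163 = 15, and 15/178 = 8%. The dropout at which 228 would leave 178 is 1 − 178/228 = 21.9%. This step does not depend on how 228 was obtained.

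**Step 4. What 228 delivers at 6 months.**
- With the 10% in 9.9: 228 × 0.90 = 205.
- With the constant hazard: dropout 1 − 0.8^0.5 = 10.6%, and 228 × 0.8^0.5 = 204.
- Wald width at 12.6% with 204 patients: 2 × 1.96 × √(0.126 × 0.874 / 204) = 9.1 points. The exact (Clopper–Pearson) width is about 9.6 points. With 205 patients the widths are practically the same.
- Margin: 228 still leaves 186 if 6-month dropout is as high as 1 − 186/228 = 18.4%, and 169 if it is 1 − 169/228 = 25.9%.

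**The case against.** The strongest reply is that nothing the study is sized for is lost. The precision target belongs to the 6-month incidence. At month 6 about 204–205 patients remain, above even the exact requirement of 186, and dropout would have to reach 18.4% before that requirement failed. The study is descriptive, with no hypothesis test or power claim. Section 9.9's conclusion that the primary endpoint can still be evaluated if early dropout is worse than expected is therefore sound. All of this stands, and it limits the point to the 18-month statement.

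It is also true that completers are not the only denominator. The safety dataset holds every enrolled patient who was dosed at least once and has data (9.7.1), and data from withdrawn patients are used (9.2.7). The protocol does not tie the whole-study incidence to FAS2. So 163 is the expected size of FAS2, not of every 18-month analysis. That does not rescue the sentence in 9.5, which speaks expressly of patients observed for the full 18 months.

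Three stronger readings are tempting, and the protocol does not support them.
- **That the 10-point target is missed because 163 is below 169.** This pairs an 18-month headcount with a 6-month incidence. No planned analysis has that combination.
- **That precision at 18 months is seriously inadequate.** The protocol sets no width target for 18 months. It also never extrapolates event incidence beyond the 12-month figure, and section 7 says the elevations occurred mostly in the first treatment year, which argues against carrying a constant event rate on to month 18.
- **That averaging a Wald size and an exact size, or inflating for 18 months when the endpoint is at 6, is a further serious flaw.** The averaging is disclosed. At 178 it misses the exact target by only about 0.2–0.3 points (22 of 178 gives 7.9–18.1%), and it has no effect with about 204 patients at month 6. Section 9.9 presents the longer horizon as deliberate caution.

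**Conclusion.** Section 9.5 contradicts itself. On its own 28.5% dropout, 228 enrolled patients yield about 163 with full 18-month follow-up, not 178. The stated yield would need 249 enrolled, or a dropout of 21.9%. Nothing elsewhere in the protocol corrects this. Section 9.9 compounds it by saying that 28.5% was used in the calculation, when 228 provides for a loss of only 21.9% if 178 are to remain.

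The contradiction rests only on reading 28.5% as the fraction of enrolled patients lost by month 18, which is how the protocol derives it. That 228 came from multiplying by 1.285 is an inference, and the conclusion does not need it. The primary 6-month precision is unaffected, on the assumption of 10–10.6% dropout by then. This is an error that should be corrected in the text. It does not put the study's main result at risk.

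**What to change.** Keep 228 and replace the last sentence of 9.5 with, for example:

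> With 228 enrolled, about 204–205 patients are expected to be observed to month 6 (10–10.6% dropout) and about 163 to month 18 (28.5% dropout). The expected 95% confidence interval width for the 6-month incidence at 12.6% is about 9.1 points (Wald) or 9.6 points (exact).

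In 9.9, replace the statement about the 28.5% allowance with one that matches: 228 enrolled leaves 178 evaluable at up to 21.9% dropout, about twice the 10% assumed at 6 months. The argument for the primary endpoint is kept and becomes correct.

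The cost is wording in two sections and a less favourable stated 18-month number, with no extra patients. If the sponsor does want 178 patients followed for 18 months, its own inputs require 249, that is 21 more. The primary endpoint does not call for them.
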